Blood, n (%) Negative or 0 ca Cells/μL "Non – Hemolyzed" or 10 ca Cells/μL (Trace) "Hemolyzed" or "Trace" "Small" (+) or 25 ca Cells/μL "Moderate" (++) or 80 ca Cells/μL "Large" (+++) or 200 ca Cells/μL Total							
Normal Abnormal CS NCS							
Bilirubin, n (%) Negative "Small " (+) "Moderate" (++) "Large" (+++) Total Not applicable							

Table 26 (Cont.) – Urinalysis – Safety population

	Total (n=xx)						
	V1	V4	V5	V7	V8	V9	V10
Bilirubin, n (%)							
Normal							
Abnormal							
CS							
NCS							
Ketones, n (%)							
"Negative"							
"Trace" (5 mg/dl) or 0.5 mmol/L							
"Small" (15 mg/dl) or 1.5 mmol/L							
"Moderate" (40 mg/dl) or 4.0							
mmol/L							
"Large" (80 mg/dl) or 8.0 mmol/L							
"Large" (160 mg/dl) or 16 mmol/L							
Total							
Normal							
Abnormal							
CS							
NCS							
Leukocytes, n (%)							
Negative or 0 ca Cells/μL							
"Trace" or 15 ca Cells/μL							
" Small" (+) or 70 ca Cells/μL							
"Moderate" (++) or 125 ca Cells/μL							
"Large" (+++) or 500 ca Cells/μL							
Total							
Not applicable							
Normal							
Abnormal							
CS							
NCS							

Table 27 – Biochemistry – Safety population

	Total (n=xx)											
	V1	V4	V5	V7	V8	V9	V10					
rea (mg/dL)												
N												
Mean Median												
Standard Deviation												
Minimum												
Maximum												
Normal												
Abnormal												
CS												
NCS												
reatinine (mg/dL)												
N												
Mean												
Median												
Standard Deviation Minimum												
Maximum												
Normal Abnormal												
CS												
NCS												
ric acid (mg/dL)												
N												
Mean												
Median												
Standard Deviation												
Minimum												
Maximum												
Normal												
Abnormal												
CS												
NCS												

	Total (n=xx)				(n=xx)											
	V1	V4	V5	V7	V8	V9	V10									
PK (U/L)																
N																
Mean																
Median																
Standard Deviation Minimum																
Maximum																
Normal																
Abnormal																
CS NCS																
DH (U/L)																
N																
Mean																
Median																
Standard Deviation Minimum																
Maximum																
Normal																
Abnormal CS																
NCS																
otal protein (mg/dL)																
N																
Mean																
Median																
Standard Deviation																
Minimum																
Maximum																
Normal																
Abnormal																
CS																
NCS																

	Total											
	(n=xx)											
	V1	V4	V5	V7	V8	V9	V10					
Total cholesterol (mg/dL)												
N Mean Median Standard Deviation Minimum Maximum												
Normal Abnormal CS NCS												
Low density lipoprotein (LE cholesterol (mg/dL) N Mean Median Standard Deviation Minimum Maximum	DL)											
Normal Abnormal CS NCS												
High-density lipoprotein (HE cholesterol (mg/dL) N Mean Median Standard Deviation Minimum Maximum	DL)											
Normal Abnormal CS NCS CS: Clinically significant: NCS: Not clinical												

	Total						
	(n=xx) V1	V4	V5	V7	V8	V9	V10
Triglycerides (mg/dL)							
N							
Mean							
Median							
Standard Deviation							
Minimum							
Maximum							
Normal							
Abnormal							
CS							
NCS							
Sodium (mEq/L)							
N							
Mean							
Median							
Standard Deviation							
Minimum Maximum							
Normal							
Abnormal							
CS NCS							
Potassium (mEq/L)							
N							
Mean							
Median							
Standard Deviation							
Minimum Maximum							
Normal							
Abnormal							
CS							
NCS							

	Total	Total (n=xx)										
	(n=xx) V1	V4	V5	V7	V8	V9	V10					
Calcium (mg/dL)												
N												
Mean												
Median												
Standard Deviation												
Minimum												
Maximum												
Normal												
Abnormal												
CS												
NCS												
Phosphorus (mg/dL)												
N												
Mean												
Median												
Standard Deviation Minimum												
Maximum												
Normal												
Abnormal												
CS												
NCS												
Chloride (mEq/L)												
N												
Mean												
Median												
Standard Deviation												
Minimum												
Maximum												
Normal												
Abnormal												
CS												
NCS												

	Total	Total (n=xx)										
	V1	V4	V5	V7	V8	V9	V10					
B12 Vitamin (pg/)												
N												
Mean												
Median												
Standard Deviation Minimum												
Maximum												
Normal Abnormal												
CS												
CS NCS												
Folic acid (ng/mL)												
N												
Mean												
Median												
Standard Deviation												
Minimum												
Maximum												
Normal												
Abnormal												
CS												
NCS												
HbA1c (%)												
N												
Mean												
Median Standard Deviation												
Minimum												
Maximum												
Normal												
Abnormal												
CS												
NCS												

	Total														
	(n=xx)	\/A	VE	V7	V0	V0	V10								
	V1	V4	V5	V7	V8	V9	V10								
asting blood insulin (μlU/mL))															
N															
Mean															
Median															
Standard Deviation															
Minimum															
Maximum															
Normal															
Abnormal															
CS															
NCS															
asting blood glucose (mg/dL)															
N															
Mean															
Median															
Standard Deviation															
Minimum															
Maximum															
Normal															
Abnormal															
CS															
NCS															

Table 28 – Tests for liver function – Safety population

	Total						
_	(n=xx)						
_	V1	V2	V3	V4	V5	V6	V10
SGOT (U/L)							
N							
Mean Median Standard Deviation							
Minimum Maximum							
Normal Abnormal							
CS							
NCS							
SGPT (U/L)							
N			-	-	-		
Mean			-	-	-		
Median			-	-	-		
Standard Deviation Minimum			-	-	-		
Maximum			-	-	-		
Normal			-	-	-		
Abnormal			-	-	-		
CS			-	-	-		
NCS			-	-	-		
Alkaline Phosphatase (U/L)							
N							
Mean Median							
Standard Deviation							
Minimum							
Maximum							
Normal							
Abnormal							
CS							
NCS							

Table 28 (Cont.) – Tests for liver function – Safety population

able 28 (Cont.) – Tests	Total (n=xx)										
	V1	V2	V3	V4	V5	V6	V10				
y-GT (U/L) N											
Mean Median Standard Deviation Minimum Maximum											
Normal Abnormal CS											
NCS											
Fotal bilirubin (mg/dL) N Mean Median Standard Deviation Minimum											
Maximum Normal Abnormal CS											
NCS											
irect bilirubin (mg/dL) N			-	-	-						
Mean Median			-	-	-						
Standard Deviation			-	-	-						
Minimum Maximum			-	-	-						
Normal			-	-	-						
Abnormal CS			-	- -	-						
NCS			-	-	-						

Table 28 (Cont.) – Tests for liver function – Safety population

	Total (n=xx)										
 	, V1	V2	V3	V4	V5	V6	V10				
Indirect bilirubin (mg/dL)											
I											
Лean											
Median											
Standard Deviation											
Minimum											
Maximum											
Normal											
Abnormal											
CS											
NCS											
Albumin (g/dL)											
N											
Mean											
Median											
Standard Deviation											
Minimum											
Maximum											
Normal											
Abnormal											
CS											
NCS											

Table 29 – Serology – Safety population

	Total	
	(n=xx)	
	V	71
	_	1
Hbs-Ag		
N		
Mean		
Median		
Standard Deviation		
Minimum		
Maximum		
Reactive		
Non-reactive		
CS CS		
NCS		
Anti-HCV		
N		
Mean		
Median		
Standard Deviation		
Minimum		
Maximum		
Reactive		
Non-reactive		
CS		
NCS NCS		

Table 30 – Hormonal evaluation – Safety population

Table 30 – Hormonal evaluation –	Total			
	(n=xx) V1	V4	V7	V10
GH (ng/mL)				
N Mean Median Standard Deviation Minimum Maximum				
Normal Abnormal CS NCS				
IGF-I (ng/mL) N				
Mean Median Standard Deviation Minimum Maximum				
Normal Abnormal CS NCS				
ACTH (pg/mL) N Mean Median Standard Deviation Minimum Maximum				
Normal Abnormal CS NCS				

Table 30 (Cont.) – Hormonal evaluation – Safety population

Table 30 (Cont.) – Hormonal evaluatio	Total (n=xx)			
	V1	V4	V7	V10
Cortisol (µg/dl), for patients without intake of N Mean Median Standard Deviation Minimum	of glucocorticoid			
Maximum Normal Abnormal CS NCS				
LH (mUI/mL) N Mean Median Standard Deviation Minimum Maximum				
Normal Abnormal CS NCS				
FSH (mUI/mL) N Mean Median Standard Deviation Minimum Maximum				
Normal Abnormal CS NCS				

Table 30 (Cont.) – Hormonal evaluation – Safety population

	Total			
	(n=xx)			
	V1	V4	V7	V10
Testosterone (ng/dl)				
N				
Mean				
Median				
Standard Deviation				
Minimum				
Maximum				
Normal				
Abnormal				
CS				
NCS				
Estradiol (pg/mL)				
N				
Mean				
Median				
Standard Deviation				
Minimum				
Maximum				
Normal				
Abnormal				
CS				
NCS				
「SH (μUI/mL)				
N				
Mean				
Median				
Standard Deviation				
Minimum				
Maximum				
Normal				
Abnormal				
CS				
NCS				
IVCJ				

Table 30 (Cont.) – Hormonal evaluation – Safety population

	Total			
	(n=xx) V1	V4	V7	V10
Free T4 (ng/dL)				
N				
Mean				
Median				
Standard Deviation				
Minimum Maximum				
Normal				
Abnormal				
CS NCS				
Prolactin (ng/mL)				
N				
Mean Median				
Standard Deviation				
Minimum				
Maximum				
Normal				
Abnormal				
CS				
NCS				

Table 31 – Hormonal evaluation associations – FAS population

Testosterone (ng/dL) at V1	Testosterone replacement therapy	Without testosterone replacement therapy	p-value
N			
Mean			
Median			
Standard Deviation			
Minimum			
Maximum			
	Hormone replacement therapy	Without Hormone replacement therapy	
Estradiol (pg/mL) at V1			
N			
Mean			
Median			
Standard Deviation			
Minimum			
Maximum			
	Levothyroxine	Without Levothyroxine	p-value
TSH (μUI/mL) at V1			
N			
Mean Median			
Standard Deviation			
Minimum			
Maximum			
Free T4 (ng/dL) at V1			
N			
Mean			
Median			
Standard Deviation			
Minimum			
Maximum			

Table 32 – Vital signs – Safety population

	Total (n=xx)									
	V1	V2	V3	V4	V5	V6	V7	V8	V9	V10
Systolic blood pressure (mmHg) N Mean Median Standard Deviation Minimum										
Maximum										
Diastolic blood pressure (mmHg) N Mean Median Standard Deviation Minimum Maximum Heart rate (bpm) N Mean Median										
Standard Deviation Minimum Maximum										
Temperature (ºC) N Mean Median Standard Deviation Minimum Maximum										

Table 33 – Physical examination – Safety population

	Total (n=xx)									
	V1	V2	V3	V4	V5	V6	V7	V8	V9	V10
Height (cm)										
N		-	-	-	-	-	-	-	-	-
Mean		-	-	-	-	-	-	-	-	-
Median		-	-	-	-	-	-	-	-	-
Standard Deviation		-	-	-	-	-	-	-	-	-
Minimum		-	-	-	-	-	-	-	-	-
Maximum		-	-	-	-	-	-	-	-	-
Weight (kg) N										
Mean										
Median										
Standard Deviation										
Minimum										
Maximum										
Findings, n (%)										
Normal										
Abnormal										
Skin and nails										
Eves										
Nose and sinuses										
Ears										
Mouth and pharynges										
Head and neck										
Thorax and lungs										
Breast										
Abdomen										
Lymphatic										
Extremities										
Vascular										
Neurological										

Table 34 – Eastern cooperative oncology group performance status – Safety population

	Total (n=xx)									
	V1	V2	V3	V4	V5	V6	V7	V8	V9	V10
ECOG result, n (%)										
0										
1										
2										
3										
4										
5										
Total										

ECOG: Eastern Cooperative Oncology Group.

Table 35 – Electrocardiogram – Safety population

	Total (n=xx)									
	V1	V2	V3	V4	V5	V6	V7	V8	V9	V10
QTcF (msec) N Mean Median Standard Deviation Minimum Maximum										
Result, n (%) Normal Abnormal without clinical significance Abnormal with clinical significance Total Consultation with cardiologist to confirm abnormal ECG?, n (%) Yes										
No Total										
If yes, cardiologist confirm QTcF interval >480msec, n (%) Yes No Total										
Patient discontinued after thorough cardiological examination. n (%) Yes No Total										

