#### **Extension Phase:**

After the Main Phase of the study (first 24 weeks of treatment), patients benefiting from treatment with pasireotide LAR will be offered the opportunity to continue to receive pasireotide LAR, based on the physician's evaluation and the patient's wishes. Patients participating in the Extension Phase will be treated with pasireotide LAR for up to 92 weeks, or until pasireotide or other effective therapy becomes commercially available, or until clinical benefit is no longer seen (whichever occurs first).

Patients enrolled in the Extension Phase will receive pasireotide LAR at the same dose used during the Main Phase. The first dose will be administered on Visit 10 (End of Main Phase [EOS] Visit, which will correspond to the Extension Phase baseline visit) and will have the next Extension Phase visit scheduled, which will occur after 28 ( $\pm$  3) days. Pasireotide LAR will be administered by the site's healthcare professional staff every 28 ( $\pm$  3) days during the Extension Phase.

Patients who will not participate in the Extension Phase must perform Visit 11 (Follow-up Visit) of the Main Phase.

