Gallbladder ultrasound scans showed that 3.7% of patients with normal gallbladder ultrasounds at baseline had gallstones after treatment with pasireotide. Colelithiasis is a known side effect associated to the therapy with somatostatin analogues, which is normally asymptomatic. Long-term data on gallbladder abnormalities related to pasireotide are not yet available.

Other details and data available from the study [CSOM230B2201] are described in the Investigator's Brochure for SC pasireotide.

Pasireotide LAR was evaluated in two further studies, one in healthy volunteers [CSOM230C2101] and one in patients, which is still ongoing [CSOM230C2110]. Preliminary data from the study in healthy volunteers [CSOM230C2101] evaluating single IM pasireotide LAR doses of up to 60 mg (N = 5 per cohort) show that pasireotide LAR was well tolerated and that the adverse events seen are comparable to those seen with octreotide LAR. The most common adverse event was diarrhea, which was sometimes associated to abdominal pain and/or flatulence. Gastrointestinal events were mild to moderate in severity. Approximately half of the subjects reported transient mild pain at the injection site. Two volunteers who received a 60 mg dose experienced mild increases in fasting blood glucose (< 123 mg/dL), with all values returning to normal 28 days after the LAR injection.

Pasireotide LAR pharmacokinetics was evaluated in healthy volunteers after a single IM injection of 40 or 60 mg. Pasireotide exposure was dose-proportional, with long-acting release phase  $C_{max}$  of  $9.6 \pm 5.1$  ng/mL and  $15.8 \pm 3.3$  ng/mL for 40 and 60 mg doses, respectively. Simulation with multiple doses suggested that this form of LAR is appropriate for monthly dosing (every 28 days). The simulated residual concentrations at steady-state ( $C_{residual,ss}$ ) were 5.5 and 11.5 ng/mL at 40 and 60 mg, respectively.

Other details and data available from the study in healthy volunteers [CSOM230C2101] are described in the [Investigator's Brochure] for pasireotide LAR.

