#### **Main Phase Treatment**

The first pasireotide LAR 60 mg IM dose will be administered on Visit 2, after all baseline evaluations are completed and the eligibility to participate in the study is confirmed. Pasireotide LAR will be administered as a depot intragluteal IM injection.

Pasireotide LAR 60 mg IM will be administered by the site staff every 28 ( $\pm$  3) days throughout the Main Phase treatment period (all patients are expected to receive 6 doses of pasireotide LAR every 4 weeks). A dose decrease to 40 mg will be allowed for safety reasons.

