#### 7.3 Treatments

The study medication administered during the study must be documented in the Dose Administration eCRF. Date and time of dose administration will be recorded in the Dose Administration Record. Compliance will be evaluated by the investigator and/or study staff on all visits. Records of study drug used, treatment administered, and intervals between visits will be kept throughout the study. Drug accountability will be registered by the field monitor during site visits and upon completion of the study.

All drugs, including over-the-counter drugs and previous therapies for the disease, taken before administration of the study drug and continuing throughout this study must be documented in the Previous / Concurrent Medication eCRF.

In the Main Phase, patients will receive the study drug on Visit 2 (Day 0) and then every 4 weeks ( $28 \pm 3$  days) thereafter, i.e., on Weeks 4, 8, 12, 16, 20. Patients who enter the Extension Phase will receive the study drug starting on Week 24, and then every 4 weeks ( $28 \pm 3$  days) thereafter, until Week 92.

All therapies administered to a patient within 4 weeks after administration of the last dose of the study medication must be documented in the Therapy Since Discontinuation eCRF.

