Eligible patients will receive pasireotide LAR 60 mg every 28 ± 3 days for 24 weeks, during the Core Phase of the study. The study is complimented by an extension. As per treating physician' discretion, patients who have benefited from the treatment with pasireotide LAR can enter an Extension Phase where they will continue to receive pasireotide LAR 60 mg at 4-week (\pm 3 days) intervals for up to 2 years or until pasireotide or other effective therapy becomes commercially available or until clinical benefit is noted (whichever comes first). Dose reductions to 40 mg will be permitted based on safety issues. In case of rapid deterioration of the visual field or sudden visual loss, the patient will be discontinued from the study.

During the Core Phase of the study, visits will be performed every 28±3 days. There will be two extra visits: Visit 3 and Visit 6.

The design of the study and a schematic of the Core Phase and Extension Phase are presented in **Figure 1** and **Figure 2**, respectively.

Figure 1 Schematic of the Pasireotide LAR Study of NFPA: Core Phase

[figure not shown]
[figure not shown]

Figure 2 Schematic of the Pasireotide LAR Study of NFPA: Core Phase

^{*}Details of efficacy and safety evaluation, presented in Table A1.

3 Population

The population for this study is adult patients with a diagnosis of NFPA who have not undergone any prior therapy (treatment-naïve) for the disease. As tumor volume changes are difficult to be evaluated in microadenomas and also because they may be misdiagnosed with incidentalomas, only patients with macroadenomas (≥ 1 cm) will be included. A total of 23 patients in 10-13 centers will be enrolled in this single-arm open-label study.

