5.3 TREATMENTS (STUDY DRUG, CONCOMITANT THERAPIES, COMPLIANCE)

The duration of exposure to the study drug, number of patients with dose adjustment (i.e., interruptions, dose changes) and dose intensity will be summarized based on FAS for core and extension period of the study.

Concomitant medications and significant non-drug therapies prior to and after the start of the study drug will be summarized by preferred terms according to the ATC class of the WHO Drug Reference List.

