Total (n=xx) HbA1c performed, n (%) Yes No Total HbA1c (%) Ν Mean Median Standard Deviation Minimum Maximum Normal Abnormal Clinically significant Non-clinically significant HbA1c ≤7% Yes No Total Fasting blood insulin (ulU/mL), n (%) Yes No Total Fasting blood insulin (ulU/mL) Mean Median **Standard Deviation** Minimum Maximum Normal Abnormal Clinically significant Non-clinically significant Fasting blood glucose (mg/dL), n (%) Yes No Total Fasting blood glucose (mg/dL) Mean Median Standard Deviation Minimum Maximum Normal Abnormal Clinically significant Non-clinically significant

Table 6 – Treatment – FAS population

	Tota (n=x															
		/2		V4		V5		V7		V8		V9		V10		ore nase
Study medication																
administered, n																
(%)																
Yes															-	-
No															-	-
Total															-	-
Dose, n (%) 60 mg															_	_
40 mg Total															-	-
Dose																
adjustment, n (%)																
Yes																
	-	-	-	-	-	-	-	-	-	-	-	-	-	-		
No Total	-	-	-	-	-	-	-	-	-	-	-	-	-	-		
Exposure																
(days) ^{a)}																
N	-	-	-	-	-	-	-	-	-	-	-	-	-	-		
Mean	-	-	-	-	-	-	-	-	-	-	-	-	_	-		
Median	-	-	-	-	-	-	-	-	-	-	-	-	_	-		
Standard	-	-	-	-	-	-	-	-	-	-	-	-	-	-		
Minimum	-	-	-	-	-	-	_	-	_	-	_	-	_	-		
Maximum	-	-	-	-	-	-	-	-	-	-	-	-	-	-		
Mean																
administration dose (mg)b)																
N	_	-	_	_	_	_	_	_	_	_	_	_	_	_		
Mean	-	-	-	-	-	-	-	-	-	-	-	-	-	-		
Median	-	-	-	-	-	-	-	-	-	-	-	-	-	-		
Standard	-	-	-	-	-	-	-	-	-	-	-	-	-	-		
Minimum	_	_	_	-	_	-	_	_	_	-	_	_	_	-		
Maximum	-	-	-	-	-	-	-	-	-	-	-	-	-	-		
Dose reduction																
before tumor volume																
reduction of at																
least 20%																
No																
Total																

a) The difference between the last administration and the first administration, in days.

b) Cumulative dose (total dose administered) divided by number administrations.

Table 7 – Magnetic resonance imaging – FAS population

	Total (n=xx)						
	V1	V4	95%CI	V7	95%CI	V10	95%CI
Volume (cm³)							
N			-		-		-
Mean			-		-		-
Median			-		-		-
Standard			-		_		_
Minimum			_		_		_
Maximum							
Tumor is not			_		_		_
Missing values			-		-		-
Volume change ^{a)}							
(cm³)							
N	-						
Mean	-						
Median	-						
Standard	-						
Minimum	-						
Maximum	-						
Percentage							
change in							
volume ^{a)} (%)							
N	-						
Mean	_						
Median	_						
Standard	_						
Minimum	_						
Maximum	-						

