Appendix 2: Statistical Tables – Extension study

Table B 1 - Patients' disposition - extension study

Total (n=xx) Patient agree to be followed for post-treatment evaluations, n (%) No Total Patient agree to be followed for survival, n (%) Yes No Total Primary reason for end of treatment, n (%) Adverse Event(s) Subject withdrew consent Lost to follow-up Administrative problems. Death Disease progression Subject is unable to tolerate the minimum pasireotide LAR dose of 40 mg. Acute or progressive vision loss confirmed by a new visual field evaluation. Uncontrolled diabetes mellitus. Clinically significant abnormal test procedure result(s). Clinically significant abnormal laboratory value(s) Protocol deviation Investigator's decision Other Study populations, n (%) Safety

Table B 2 – Concomitant medication – extension study – FAS population

Table B 2 – Concomitant med	dication – extension study – FAS population	
	Total	
	_(n=xx)	
Any medication or significant nor	ı-drug therapy, n (%)	
Yes		
No		
Total		

Table B 3 – Treatment – extension study – FAS population

	Total (n=xx)					
	V13	V16	V19	V22	V25	Extension phase
Study medication administered, n (%)	-					•
Yes						_
No						_
Total						-
Dose, n (%)						
60 mg						-
40 mg						-
Total						-
Exposure (days) ^{a)}						
N						
Mean						
Median						
Standard Deviation						
Minimum						
Maximum						
Mean administration dose (mg)b)						
N						
Mean						
Median						
Standard Deviation						
Minimum						
Maximum						

a) The difference between the last administration and the first administration of extension phase, in days.
b) Cumulative dose (total dose administered in the extension phase) divided by number administrations (extension phase).

Table B 4 – Magnetic resonance imaging – FAS population

	Total			
	(n=xx)			
	V16	V22	V28	
Volume (cm³)				
N			-	
Mean			-	
Median			-	
Standard Deviation				
Minimum				
Maximum			-	
Tumor is not visible Missing values			-	
iviissing values			-	
Volume change ^{a)} (cm ³)				
N Mean				
Median				
Standard Deviation				
Minimum				
Maximum				
Percentage change in volume ^{a)} (%)				
N				
Mean				
Median				
Standard Deviation				
Minimum				
Maximum				
Reduction of tumor volume ^{b)} , n (%)				
Yes No				
≥20% tumor volume reduction ^{c)} , n (%)				
Yes				
No Total				
Total				
≥20% tumor volume reduction using LOCF method, n (%)				
Yes				
No				
Total				
For patients who achieved a reduction in tumor volume				

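### Exposure counted as last minus first injection drops the final 28-day depot interval, and the SAP does not say which phase owns the Visit 10 injection

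*SAP*

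**What the plan says.** SAP Section 5.3 plans to summarise duration of exposure, and says that "dose intensity will be summarized based on FAS for core and extension period of the study". Neither that section nor protocol Section 10.3 defines duration. The only definitions are table footnotes:

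- SAP Table 6 (core), footnote a: "The difference between the last administration and the first administration, in days".
- SAP Table B 3 (extension), footnote a: "The difference between the last administration and the first administration of extension phase, in days".

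The regimen is set out in SAP Section 2: "Eligible patients will receive pasireotide LAR 60 mg every 28 ± 3 days for 24 weeks, during the Core Phase of the study". In the protocol (Section 6.4, Main Phase Treatment), "all patients are expected to receive 6 doses of pasireotide LAR every 4 weeks". After Day 0 these fall, per protocol Section 7.3, "i.e., on Weeks 4, 8, 12, 16, 20".

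The Visit 10 injection (Day 168) is given only to patients entering the extension. On that phase's dosing, the protocol synopsis says: "The first dose will be administered on Visit 10 (End of Main Phase [EOS] Visit, which will correspond to the Extension Phase baseline visit". However, the synopsis also lists it among the Main Phase medication visits, and both visit schedules (protocol Tables 7-1 and 7-2) show it as injection 7. SAP Table 6 has a V10 column; the columns of Table B 3 start at V13.

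**The concern.** With a four-weekly depot, treatment continues through the interval after each injection. Last minus first counts the gaps between injections and so loses one interval per patient. The relative loss is greatest in patients who stop early. A patient who qualifies for the full analysis set with a single injection is shown with zero days.

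The SAP also disagrees with itself. Section 5.5.3.1 treats an event as treatment-emergent if it starts up to 28 days after the last administration, while the exposure row excludes those same days. A patient whom Table 1 records as having completed the planned treatment duration would appear in Table 6 four weeks short of it.

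The second difficulty is Visit 10. The core footnote sets no phase limit, whereas the extension footnote does. If the V10 date counts as the last administration in Table 6, core exposure reflects extension entry, which rests on the physician's view of benefit, as well as core treatment.

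**Working it through.** **Inputs**

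- Dosing interval: 28 days (SAP Section 2). The protocol's pharmacokinetic background supports it: "Simulation with multiple doses suggested that this form of LAR is appropriate for monthly dosing (every 28 days".
- Core injections: Days 0, 28, 56, 84, 112 and 140 (protocol Table 7-1 and Section 7.3).
- Visit 10 injection, extension entrants only: Day 168.
- Last extension injection: Week 92, Day 644 (SAP Table A 2).

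**The plan's own duration.** 6 injections × 28 days = 168 days = 24 weeks. This matches the stated core duration, so the documents themselves allot 28 days to each injection.

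**Footnote a in the core phase.** For k injections on schedule, the footnote gives 28 × (k − 1) days, against 28 × k days treated. The relative shortfall is 1/k.

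| Core injections | Footnote (days) | Treated (days) | Shortfall |
|---|---|---|---|
| 1 | 0 | 28 | 100% |
| 2 | 28 | 56 | 50% |
| 3 | 56 | 84 | 33.3% |
| 4 | 84 | 112 | 25% |
| 5 | 112 | 140 | 20% |
| 6 | 140 | 168 | 16.7% |

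**Extension.** Footnote: 644 − 168 = 476 days. Treated: 476 + 28 = 504 days = 72 weeks, which is Week 24 to Week 96.

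**Visit 10 counted in core.** An entrant has 168 − 0 = 168 days; a completer who does not enter has 140. Both had the same six core injections. If a share f of completers enters, their mean core exposure is 140(1 − f) + 168f: 140 days if none enter, 154 if half do, 168 if all do.

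**Visit 10 left out of core.** Core 140 + extension 476 = 616 days. Treatment through Week 96 is 672 days. The 56 missing days are Days 140 to 168, which fall in neither phase, and the 28 days after Day 644.

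**Check of the repair.** Core with V10 assigned to the extension: 140 − 0 + 28 = 168 days, whether or not the patient enters. One injection: 0 + 28 = 28. Full extension: 504. Total: 168 + 504 = 672, with no gap or overlap on schedule. Adding 28 days without reassigning V10 would give entrants 168 + 28 = 196 core days, so both changes are needed.

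**Visit windows.** If every interval lay at a limit of its ±3 days, six injections would span 5 × 25 = 125 to 5 × 31 = 155 days. Individual values move, but the omission of the final interval remains.

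**The case against.** The strongest reply is that nothing important depends on this row. The adverse event tables use patients or events as denominators, SAP Section 5.5.4 plans counts and percentages, and neither document plans an exposure-adjusted rate. The mean dose in Tables 6 and B 3 is divided by number of administrations, not by days. All of this stands. A reader might infer that exposure time is the planned safety denominator, or that early discontinuers' events would be lost or misjudged; the documents do not support either. The treatment-emergent window already extends past the last injection, and Table 6 shows administration and dose visit by visit.

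A reader might also infer that the figure is wrong for every patient. It is not. With V10 counted, an on-schedule completer who enters the extension gets 168 core days, the correct number, though only because a dose that the protocol elsewhere calls the first extension dose was included.

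Nor is dependence on extension entry certain. The V10 column follows the protocol's own Main Phase schedule, and nothing says that V10 must be the last core administration. What stands is that the SAP leaves this open and that neither reading works under the present footnotes.

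Finally, last minus first is explicit and reproducible, and adding 28 days is a convention. The documents also use 56 days after the last dose, but as a safety follow-up period. The 28-day figure is both the dosing interval and the treatment-emergent window. An uncapped addition would overstate exposure in a patient who dies or is last seen within 28 days of an injection, so a cap is needed.

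**Conclusion.** The point holds as a reporting error of limited reach. The stated rule understates exposure by one 28-day interval: 140 instead of 168 days for a six-injection core completer, 0 instead of 28 for a one-injection patient, and 476 instead of 504 for a full extension. It is inconsistent with the 24-week regimen and with the SAP's treatment-emergent window. Core exposure as written can also be 140 or 168 days for identical core treatment, if V10 is taken as the last core administration; if it is not, Days 140 to 168 are unassigned.

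The effect is confined to the descriptive exposure rows of Tables 6 and B 3. The figures assume injections on the scheduled days and a nominal 28 days of treatment per injection. It should be corrected because the rule produces a misleading number and is easy to change.

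**What to change.** Replace footnote a in Tables 6 and B 3 with one derivation: within each phase, exposure in days is the last injection date minus the first injection date, plus 28, truncated at death or last contact if earlier. For this derivation, assign the Visit 10 injection to the extension only, and end core exposure at the Visit 10 injection date for patients who enter. The V10 column in Table 6 can stay if a note says that it does not contribute to core exposure.

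The cost is two footnotes and a small change to the derivation code, with no new data and no change to treatment or visits. The change belongs in the SAP itself, because Section 7 requires departures from its definitions to be accepted by the sponsor and documented. The small downside is that 28 days is nominal: with the ±3-day windows, a patient's actual interval may be a few days shorter or longer.
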